Protocol ID: IRB-HSR# 21926

Date: 11/01/2019

Knee Biofeedback Rehabilitation Interface for Game-based Home Therapy ("KneeBRIGHT")

Phase II

Protocol

Osteoarthritis (OA) is the leading cause of disability in the United States. As osteoarthritis is associated with the lower limb muscle weakness, rehabilitation focused on quadriceps and other lower extremity muscle strengthening is a well-established treatment for patients with knee OA. However, patient adherence to exercise routines is low due to the lack of guidance regarding optimal protocols, and poor engagement during the repetitive routines that patients find tedious and boring.

Long-term goal of this study is to improve knee OA outcomes through effective and motivating rehabilitation exercises. The Knee Biofeedback Rehabilitation Interface for Game-based Home Therapy ("KneeBRIGHT") system combines electromyography (EMG) biofeedback with video game therapy (VGT) to provide knee OA patients with an engaging, effective tool for conducting rehabilitation exercises at home. KneeBRIGHT aims to motivate patients with knee OA to conduct regular muscle strengthening exercise through an engaging, EMG-driven video game therapy.

Participants with age from 40-75, with independent ambulation and with the diagnosis of knee OA made by x-ray and a score of at least 2 (out of 4) on the Kellgren-Lawrence OA radiographic classification system will be included in the study. Participants with psychiatric or cognitive impairment (e.g., dementia), symptomatic spine, hip, ankle, or foot disease other than OA that would interfere with assessment of the knee will be excluded. Participants with balance or vestibular disorders, peripheral neuropathy, skin conditions that prevent EMG electrode placement, prisoner, pregnant women (by report), non-English-speaking, individuals who are visually and/or hearing impaired will also be excluded.

Eligible participants will be randomized to two groups: (1) KneeBRIGHT group; (2) Standard rehabilitation group. Both groups will undergo baseline and follow up assessment to measure the patient-reported outcomes, thigh muscle strength, and balance. Participants in both groups will undergo a 12-week program including 3 exercise sessions per week that includes a combination of in-person and at home sessions (Table 1).

Table 1 Study schedule for participants visits over 12 weeks

	Visit 1 (Screening)	Visit 2 (Baseline)	Visit 3-38	Follow-up
Study Week	0	0	1-12	13
Informed Consent	x			

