Review study eligibility	x	x		
Medical History	x			
Strength, Balance & Endurance testing		x		
Questionnaires		x		x
Rehabilitation Exercises			x	x

Both groups will undergo same rehabilitation protocol which will begin with sessions supervised in the clinic by the study team physical therapist and gradually home sessions will be added. Participants in KneeBRIGHT group will perform the quadriceps strengthening exercises with the video-games based activities. The EMG biofeedback units and video game w/laptop will be provided to the subjects for home use. Subjects will receive instruction on how to apply the EMG biofeedback unit and use of the video game. KneeBRIGHT Game Activities consists of an introduction of the player to the virtual world and the missions, the player customizes the personal avatar and completes a series of calibration contractions and practice exercises to gain familiarity with the game controls. Through the EMG system, a player's muscle contractions translate into physical movements of the avatar and control of vehicles within the virtual environment. Each quest-type challenge is designed to permit play in a seated, supine, supported standing, or freestanding position, based on an individual's physical status. User interactions with the game incorporate knee extension exercises and functional movements that provide optimal therapeutic benefits.

Participants in both groups will undergo combination of home and in clinic sessions. Protocol will start with six clinic visits in order to maximize familiarity with the exercise routines and equipment. Home sessions will be added after 2 weeks in rehabilitation (Table 2). The sessions will consist of warm up, strengthening, balance, precision and gentle stretching exercises. Strengthening exercises will be focused on quadriceps, hamstring, calf and gluteal muscles. Stretching exercises will be focused on quadriceps, hamstring and calf muscles. Progression will be guided by the rehabilitation principles and participants response to the exercise. The amount of these exercises will depend on how they make the subject feel. The rehabilitation program will allow the subject to increase the amount of exercise they can perform. Exercises will be limited if the subject feels discomfort. Overall, protocol will consist of 36 sessions in total, 20 in clinic sessions and 16 home-based sessions.

Table 2 Weekly schedule for patients for in clinic and home-based therapy sessions

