	One Hour Exercise Sessions	
	In clinic session	Home-based session
Week 1	3	0
Week 2	3	0
Week 3	2	1
Week 4	2	1
Week 5	2	1
Week 6	2	1
Week 7	1	2
Week 8	1	2
Week 9	1	2
Week 10	1	2
Week 11	1	2
Week 12	1	2
TOTAL	20	16

Pre and post intervention outcome measures will be compared to explore the effectiveness. Technology acceptance will also be studied in patients randomized to KneeBRIGHT group.

Overall, KneeBRIGHT has the potential to significantly enhance OA rehabilitation by improving functional recovery through physical practice of specific, adaptive exercise and promoting adherence through fun games and performance feedback. Use of the KneeBRIGHT system in teletherapy may increase access to remote/underserved areas and extend the range of existing rehabilitation facilities.

Statistical analysis

Knee function assessed by composite KOOS score prior to the study will be compared to the KOOS score recorded post-intervention to test the primary hypothesis that patients conducting the KneeBRIGHT exercise will significantly improve knee function compared to the control group. Pre-intervention KOOS scores measures will be subtracted from the post-intervention scores to produce a set of delta values. These delta values will be analyzed via Analysis of Covariance (ANCOVA). A $p \leq 0.05$ decision rule will be utilized as the rejection criterion.

Questionnaire results will be used to test the hypothesis that patients using the KneeBRIGHT system demonstrate increased levels of engagement compared to those conducting a conventional exercise routine. The questionnaire scores will be tallied to produce composite scores. These composite scores will be analyzed via a linear mixed model. A $p \leq 0.05$ decision rule will be used as the null hypothesis rejection criterion.

Timing data from the home visits will be analyzed by comparing the minutes of exercise with the KneeBRIGHT system to minutes of exercise with the standard exercise regimen in the control group to

test the hypothesis that exercise duration is greater with the KneeBRIGHT system. Mean usage time on each system will be analyzed via Student's paired *t*-test, with $p \leq 0.05$ as the null hypothesis rejection criterion.

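### Home exercise minutes are compared between two separately randomised groups by a paired t-test; a between-arm linear model with baseline KOOS as covariate fits the design and probably gains precision

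*Combined protocol and SAP*

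**What the plan says.** The third paragraph of the Statistical analysis section sets home exercise minutes on KneeBRIGHT against "minutes of exercise with the standard exercise regimen in the control group", to "test the hypothesis that exercise duration is greater with the KneeBRIGHT system". The method is: "Mean usage time on each system will be analyzed via" a Student's paired t-test, with a 0.05 criterion whose sidedness is not stated. No covariate is named.

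The design is parallel: "Eligible participants will be randomized to two groups: (1) KneeBRIGHT group; (2) Standard rehabilitation group". No crossover or matching is described.

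The first paragraph of the same section has composite KOOS recorded before the intervention and analyses KOOS change by ANCOVA, without listing the covariates. Table 1 also has a baseline entry for "Strength, Balance & Endurance testing". On how much participants exercise, the protocol says: "The amount of these exercises will depend on how they make the subject feel".

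**The concern.** The named test does not match the comparison. A paired t-test needs two measurements on the same person or on a matched pair, and here each participant contributes minutes under one system only. If the arms differ in size, the test cannot use everyone. If they are equal in size, the result depends on an arbitrary pairing.

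Changing to an independent-samples t-test would solve that, but it would still leave out baseline KOOS. If knee function at entry partly explains how long people exercise at home, that variation stays in the error term, and the comparison is less precise than the collected data allow. Since the sentence has to be rewritten anyway, the question is whether the replacement should carry a baseline covariate.

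**Working it through.** **Inputs.** From the documents: two randomised arms, significance level 0.05, baseline composite KOOS collected, and 16 home sessions headed as one hour each in Table 2 (16 × 60 = 960 scheduled minutes). Not in the documents: sample size, SD of minutes, target difference, power, and R. There is therefore no planned figure to reproduce. Everything below is illustrative, takes the test as two-sided, and assumes values for R and the number per arm.

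**Step 1: cost of the paired test.** With two independent arms of equal size n and arbitrary pairing, the degrees of freedom fall from 2n − 2 to n − 1. For an effect that the independent-samples test detects with 80% power, noncentral t calculations give:

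| n per arm (assumed) | Independent test | Paired test |
|---|---|---|
| 10 | 80% | 75.1% |
| 15 | 80% | 77.0% |
| 25 | 80% | 78.3% |
| 50 | 80% | 79.2% |

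The power cost is modest. The main fault is that the pairs do not exist.

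**Step 2: gain from the covariate, before its cost.** Adjusted variance ÷ unadjusted variance = 1 − R².
- R = 0.1: 1 − 0.01 = 0.99
- R = 0.3: 1 − 0.09 = 0.91
- R = 0.5: 1 − 0.25 = 0.75

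On a power scale, take an assumed standardised difference of 0.5 with 63 per arm, which gives 80.1% unadjusted. Power becomes 80.5% at R = 0.1, 83.7% at R = 0.3 and 90.0% at R = 0.5. The number per arm needed for the same 80% is 63, 58 and 48 respectively.

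**Step 3: cost of one covariate.** With total N and k covariates, estimating them inflates the variance on average by (N − 3)/(N − k − 3). For k = 1 this is (N − 3)/(N − 4).
- 15 per arm, N = 30: 27/26 = 1.038
- 30 per arm, N = 60: 57/56 = 1.018

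Net variance ratio = (1 − R²) × (N − 3)/(N − 4):

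| R (assumed) | 15 per arm | 30 per arm |
|---|---|---|
| 0.1 | 0.99 × 1.038 = 1.03 | 0.99 × 1.018 = 1.01 |
| 0.3 | 0.91 × 1.038 = 0.94 | 0.91 × 1.018 = 0.93 |
| 0.5 | 0.75 × 1.038 = 0.78 | 0.75 × 1.018 = 0.76 |

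Break-even is where R² = 1/(N − 3): R = √(1/27) = 0.19 at 15 per arm and √(1/57) = 0.13 at 30 per arm.

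**Step 4: why one covariate and not two.** With k = 2 the factor is (N − 3)/(N − 5). At 30 per arm this is 57/55 = 1.036, with break-even at √(2/57) = 0.19. At 15 per arm it is 27/25 = 1.08, with break-even at √(2/27) = 0.27. A second covariate must add real prediction to repay this.

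**The case against.** The strongest reply is that nothing in the documents ties baseline KOOS to home minutes. A reader might infer the link from the statement that exercise amount depends on how the subject feels. That statement describes response during the programme, after randomisation and possibly affected by arm. It says nothing about status at entry, and the amount it refers to could be load or repetitions as well as minutes. Other features point to a small R. Home sessions are scheduled at one hour, so minutes may vary mainly through missed or shortened sessions. The introduction attributes low adherence to lack of guidance and tedium, not to knee severity. The game can also be played in positions suited to physical status. This stands, and it is why the gain can only be called likely.

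A reader might also infer that chance imbalance in baseline severity is a further harm. It is not. Randomisation leaves no bias on average, and the unadjusted standard error already includes that variation, so counting it beside the precision loss would count it twice.

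Nor does Table 1 support endurance as a second covariate. Endurance appears there only as part of a row label, with no test, unit or score described.

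Against these points, the plan expects minutes to differ between participants, since it tests duration, and it already uses ANCOVA for KOOS change. It is reasonable, though not documented, to expect knee function at entry to bear on exercise time in knee osteoarthritis.

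**Conclusion.** The paired test does not fit a parallel-group comparison and needs replacing. Adding baseline KOOS to its replacement is an inexpensive efficiency improvement on a non-primary hypothesis. An independent-samples test without covariates would be valid, so the missing adjustment is neither a bias nor an error.

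The stronger reading, that precision is demonstrably being lost and could be recovered at no cost, is not supported, because R and the sample size are not given. After the cost of one covariate, the illustrative range runs from a 3% variance increase (R = 0.1, 15 per arm) to a 24% reduction (R = 0.5, 30 per arm). The possible loss is small and the possible gain larger, which favours pre-specifying the covariate.

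**What to change.** Replace the paired t-test sentence with a linear model of each participant's home exercise minutes on randomised arm, with baseline composite KOOS as the single pre-specified covariate. Report the adjusted between-arm difference in minutes with a 95% CI, and keep an unadjusted independent-samples comparison as supportive. In the same sentence, define the per-participant summary of minutes, including how missed home sessions count, and state whether the test is two-sided. Do not adjust for discomfort during the programme, because it arises after randomisation.

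The cost is a change of SAP wording, one model and one degree of freedom. No new data, visits or participants are needed. The covariate should be fixed before outcome data are examined.

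### Adherence is a claimed potential benefit, but completed home sessions are not measured and mean usage time has no stated denominator or rule for skipped sessions

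*Combined protocol and SAP*

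**What the plan says.** The opening of the protocol gives the problem as "patient adherence to exercise routines is low", and attributes it to lack of guidance and to poor engagement with tedious routines. The closing paragraph before the Statistical analysis section lists two things the system may achieve: "improving functional recovery through physical practice of specific, adaptive exercise and promoting adherence through fun games and performance feedback".

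On exercise, the protocol states: "Both groups will undergo same rehabilitation protocol". Table 2 is headed "One Hour Exercise Sessions" and schedules 20 clinic and 16 home sessions over 12 weeks. The text before Table 2 lets the amount of exercise vary with how the participant feels, so one hour is a nominal length.

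The Statistical analysis section has three tests:
- The primary hypothesis, on composite KOOS, is that "patients conducting the KneeBRIGHT exercise will significantly improve knee function compared to the control group".
- An engagement composite from questionnaires is analysed by linear mixed model.
- Home exercise minutes are compared between arms, under the hypothesis that duration is greater with KneeBRIGHT. The summary is described only as "Mean usage time on each system will be analyzed", and the test named is a paired t-test.

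No test, endpoint or threshold refers to the number or proportion of home sessions completed.

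**The concern.** The two arms have the same home schedule and the same nominal session length. A large part of any adherence difference should therefore show in how many of the 16 home sessions are done, and less of it in how long each one lasts. The plan has no count of sessions done. Its one quantitative measure of home exercise is a mean with no denominator. If that mean is taken over completed sessions only, a participant who skips most sessions but finishes the rest looks the same as one who does them all.

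At stake is whether the trial can support its adherence claim. Depending on a choice not yet written down, the timing test could show a difference in adherence, miss it or reverse it. An open denominator also leaves the definition to be settled after the data have been seen.

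**Working it through.** **Step 1. Reproduce the schedule (Table 2).**
- Clinic: 2 weeks × 3 + 4 weeks × 2 + 6 weeks × 1 = 6 + 8 + 6 = 20.
- Home: 2 weeks × 0 + 4 weeks × 1 + 6 weeks × 2 = 0 + 4 + 12 = 16.
- Total: 20 + 16 = 36, as the protocol states.
- Scheduled home time per participant: 16 × 60 = 960 minutes, the same in both arms.

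**Step 2. Apply the possible definitions of mean usage time.** Let k be home sessions completed and m the minutes per completed session.
- Per completed session: km / k = m. The count k cancels.
- Per scheduled session, skipped = 0: km / 16.
- Total per participant: km.
- Completion: k / 16.

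The documents give no completion rates, so the values of k and m below are assumptions. Each pair is KneeBRIGHT v control.

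| k | m (min) | Per completed session | Per scheduled session | Total minutes | Completion |
|---|---|---|---|---|---|
| 14 v 10 | 60 v 60 | 60 v 60 | 52.5 v 37.5 | 840 v 600 | 87.5% v 62.5% |
| 12 v 8 | 60 v 60 | 60 v 60 | 45 v 30 | 720 v 480 | 75% v 50% |
| 16 v 8 | 60 v 60 | 60 v 60 | 60 v 30 | 960 v 480 | 100% v 50% |
| 16 v 8 | 55 v 60 | 55 v 60 | 55 v 30 | 880 v 480 | 100% v 50% |
| 8 v 14 | 60 v 60 | 60 v 60 | 30 v 52.5 | 480 v 840 | 50% v 87.5% |

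In every row with equal session length, the completed-session mean shows no difference, whichever arm adheres better. In the 16 v 8 row with 55 v 60 minutes it reverses the order: the arm with the higher mean did 1 − 480/880 = 45% less exercise.

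**Step 3. What total minutes can and cannot show.** Total minutes fall when sessions are skipped, so they respond to adherence. They do not isolate it: 480 minutes may be 8 sessions of 60 minutes or 16 sessions of 480/16 = 30 minutes. A separate count tells these apart.

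**Step 4. Illustrative power.** Every input is assumed: beta-binomial completion, session length about 52 minutes (SD 6, capped at 60) in both arms, correlation of completion within participant from 0.3 down to 0.05, and a two-sided independent-groups test at 5%.
- Mean over completed sessions: rejects about 5% of the time. This follows from setting session length equal in the two arms.
- Total minutes with zeros, 80% v 60% completion: about 0.53 to 0.93 with 15 per arm, and 0.83 to 0.99 with 30 per arm.
- Total minutes with zeros, 80% v 70% completion, 30 per arm: about 0.31 to 0.75.

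A larger sample does not help the completed-session mean, because it does not contain the count.

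**The case against.** The strongest reply is that the plan nowhere says that usage time is averaged over completed sessions. It speaks of comparing minutes of exercise between arms, and a natural reading is each participant's home minutes averaged over the participants in the arm. A skipped session then lowers the result, and the 880 v 480 example is ranked correctly. This stands. A reader might infer that the plan discards skipped sessions and so cannot answer the adherence question, but the text supports only that the denominator and the skipped-session rule are missing.

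Three further objections also stand in part:
- A reader might take session length as fixed by design. One hour is nominal: the protocol lets the amount vary with tolerance, and a hypothesis of greater duration presupposes variation.
- A reader might take adherence to be what the trial was built to test. It is background and one of two potential benefits; the stated hypotheses concern knee function, engagement and exercise duration. The engagement questionnaire is related, since poor engagement is named as a cause of low adherence, but the plan does not use it to count sessions.
- The documents do not describe how home minutes are recorded, least of all in the control arm, so it cannot be assumed that session counts are already available.

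None of these supplies the missing denominator or the missing count.

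**Conclusion.** The point holds as a gap in definition and is worth correcting. The plan offers adherence as a potential benefit, measures no completed sessions, and leaves its home-exercise summary open to definitions that can disagree in size and even in direction. On the completed-session reading an adherence difference would be missed or reversed (55 v 60 minutes against totals of 880 v 480). On the total-minutes reading it would be captured in part. The documents do not establish which reading is meant, so it would go too far to say that the trial will fail to detect an adherence effect.

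The arithmetic on definitions needs only the 16 scheduled home sessions and the assumed counts shown. The power figures are illustrations, because no sample size, completion rate or spread is given. Naming a paired test for two randomised, independent arms is a further flaw in the same sentence, and the same rewording can remove it.

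**What to change.** Replace the usage-time sentence in the Statistical analysis section with two defined measures for every randomised participant:
- Home exercise minutes summed over the 16 scheduled home sessions, with zero for each session not done. Dividing by 16 gives minutes per scheduled session and does not alter the comparison.
- Home sessions completed out of 16, reported as the measure of adherence.

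Compare both between arms as independent groups in place of the paired t-test, and settle the definitions before any outcome data are examined.

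The cost is a few lines of analysis-plan text, with no change to treatment, provided that home timing is recorded session by session. The sponsor needs to confirm this, because the documents mention home timing data but not how they are captured. The main downside is that a session done but not recorded counts as zero. If recording is more complete in one arm, for example because the device logs use and the control arm relies on self-report, the comparison would be biased. The sponsor should therefore confirm that timing is recorded the same way in both arms and check the home records at the clinic visit, which Table 2 schedules in every week.
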